RRT Fidelity. We will be able to electronically track whether reports go out and whether they are timely/accurate. In addition, although we do not have a scalable way to track outreach attempts for 6,000 subscribers in Study 2, we will carefully document implementation processes and meet monthly with CareSource and intervention agencies, hear their experiences, offer feedback, and help problem-solve challenges. We will keep structured implementation process notes from these meetings for further analysis. Provider names will be included in the notes. All data from the implementation process feedback will be securely stored in REDCap. No names or identifiers will be used in any published works and will be accessible only to authorized research staff. Testing our service engagement mechanism will also help to elucidate steps in the causal chain (i.e., from the reports, to services provided, to suicide attempts).

Assignment to “intervention” and “control” conditions in the two studies is independent: participants may receive Intervention-Intervention, Intervention-Control, Control-Intervention, or Control-Control. Participants will be followed for 6 months following jail release using claims data.

C4. Data Analysis

Twelve months of historical (i.e., prior to arrest) and six months of prospective (i.e., after release) jail and Medicaid claims data will be extracted from CareSource’s Jail-Medicaid database for each participating subscriber for all measures, including demographics, diagnoses, suicide attempts, service use, number of arrests, dates of jail bookings/releases, and days incarcerated. Each eligible subscriber will be followed for 6 months following the index release from jail using claims data. CareSource will provide a limited dataset to the P50 Center (at MSU) that will be de-identified and analyzed by Center statisticians. Because these statisticians are employed by Brown University, an IAA will be established with both MSU and Brown University.

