For Aim 1, we will assess total number of subsequent attempts using the already-developed Mental Health Research Network (MHRN) algorithm for extracting MT suicide attempt information from claims data.^{10-12,48-58} The main effectiveness analysis is planned as a comprehensive model (i.e., including all 43,000 subscribers) evaluating Study 1 and Study 2 intervention effects, which provides optimal power and the ability to test interactive effects of interventions. All analyses will covary baseline (i.e., past year) values of dependent variables, and will use days incarcerated in the 6 months after the index jail release as an offset. **MT suicide attempts.** The main analysis framework will be logistic regression with the cumulative risk of a claims-data-identified suicide attempts requiring medical treatment over six months post-release as the outcome. We will secondarily use a negative binomial model and a count outcome for the number of MT suicide attempts. Our models will include robust standard errors due to clustering at the agency level. We will adjust for study month, and include indicator variables reflecting: (1) Study 1 intervention condition (i.e., CC or CAU); (2) inclusion in Study 2; (3) Study 2 intervention condition (i.e., RRT or Control). The ***hypothesis that the Study 1 intervention (CC) reduces suicide attempts*** is evaluated with magnitude and significance of parameter estimate associated with random assignment to the Study 1 intervention. The ***hypothesis that the Study 2 intervention (RRT) reduces suicide attempts*** is tested with the parameter estimate associated with exposure to the level 2 intervention. ***The hypothesis that the addition of flags and recommendations to provide SPI*** for individuals with past 12 months claims data identified suicide attempts (one component of the Study 2 intervention) ***will further reduce suicide attempts*** will be tested through the interaction between past history of suicide attempt and being in the Study 2 intervention condition. Identical analyses will be conducted for the other outcomes (all count outcomes): all cause injury and poisoning, outpatient BH visits, calls to CMS line, suicide-related ED visits/hospitalizations, and returns to jail detention. ***Exploratory.*** We will evaluate the interaction of Study 1 and Study 2 interventions by including an interaction term of the two indicators. ***Moderators.*** We will test sex, race/ethnicity, past suicide attempt (y/n), past 6-month BH visit (y/n), past 12-month arrest (y/n), area Deprivation Index,⁵⁹⁻⁶⁰ Mental Health Professional Shortage Area (HPSA)

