
score,⁶¹⁻⁶² and per capita incarceration (by zip code) as moderators of intervention effects on suicide attempts, using $p < .01$.

Aim 2 will be analyzed by examining the number of outpatient BH claims in the 6 months following the index jail release and number of calls to the CMS line as mediators of the intervention/s effects on suicide attempts by adding this variable to our effectiveness model. Mediation is revealed by the extent to which the intervention effect parameter estimates change with the addition of the putative mediator. We will use bootstrap methods to estimate 95% uncertainty intervals around the mediated effect.

For Aim 3, our grants accounting will capture the costs of the CC mailings. Treatment received as part of the intervention and CAU conditions (including outpatient, inpatient, and ED mental health and suicide-related medical care visits) will be tracked using claims data. Costs of CAU will be computed as CareSource payments plus co-pay and deductibles. We will add training costs for providers but exclude other research costs that would not be incurred if RRT was standard care. The primary cost-effectiveness (CE) measure, computed from a societal perspective for each intervention arm, will be the program cost divided by the sum of suicide attempts prevented. We also will assess the net cost of the program from a MCO perspective. That measure will exclude patient payments from costs.

Costs (and savings) in future years will be discounted to present value in the year of jail release using the 3% discount rate recommended by the Second Panel on Cost-Effectiveness in Health and Medicine.⁶³ We will bootstrap the 95% uncertainty interval around the CE ratio. Analyses from the MCO perspective will compute the change in claims costs by running a generalized linear model (GLM) with gamma, inverse Gaussian, or Poisson variance based on data distribution, the log link function, and robust standard errors.⁶⁴ We will use a 2-part GLM unless less than 5% of patients have zero costs. Independent variables will include treatments received, demographics, Elixhauser co-morbidities,⁶⁵ and days of MCO coverage after jail discharge. We also will track the MCO separation rate post-discharge by group.

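### Aim 2 mediation adjusts for past-year attempts but names no diagnosis, comorbidity or baseline service-use covariate, so confounding of visits and calls with attempts can bias it in either direction

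*Combined protocol and SAP*

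**What the plan says.** Section 2.C4 (Data Analysis) describes Aim 2 as "examining the number of outpatient BH claims in the 6 months following the index jail release and number of calls to the CMS line", treated as mediators of the intervention effects on suicide attempts "by adding this variable to our effectiveness model". The estimate is a change in coefficient: "Mediation is revealed by the extent to which the intervention effect parameter estimates change with the addition of the putative mediator". Bootstrap 95% intervals are planned.

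The effectiveness model is set out under Aim 1 in the same section. On baseline adjustment it says "All analyses will covary baseline (i.e., past year) values of dependent variables"; when the dependent variable is suicide attempts, that means past-year attempts. It continues: "We will adjust for study month, and include indicator variables reflecting: (1) Study 1 intervention condition (i.e., CC or CAU); (2) inclusion in Study 2", followed by the Study 2 condition. There is also an offset for time incarcerated after release.

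No diagnosis, comorbidity, or baseline visit or call count is named for this model or for Aim 2. Such variables do appear elsewhere in Section 2.C4. Twelve months of pre-arrest data are extracted "for all measures, including demographics, diagnoses, suicide attempts, service use, number of arrests". A recent BH visit is listed as a candidate moderator, and Elixhauser comorbidities enter the Aim 3 cost model. The documents state no assumption about mediator-outcome confounding and plan no sensitivity analysis for it.

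**The concern.** Letters are randomised to subscribers, and agencies are randomised to start dates. How often a subscriber attends visits or calls the line is not randomised. Reading mediation from the change in the intervention coefficient is valid only if, given the covariates in the model, nothing else drives both service use and attempts. If something does, the mediator's coefficient absorbs it, and the change in the intervention coefficient carries the same bias. The bootstrap measures sampling error only, so its interval would be centred on the biased value. This is separate from the time order of visits and attempts and would remain if that order were fixed.

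Aim 2 is the test of the service-engagement mechanism. The RRT Fidelity paragraph (Section 2.C2) relies on it to trace the path from reports to services to attempts, and says outreach itself cannot be tracked at scale for the roughly 6,000 Study 2 subscribers. A biased mediated effect could understate or overstate what re-engagement achieves.

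**Working it through.** The plan gives no effect size or power for Aim 2, so there is no stated figure to reproduce. The check has two parts: what the model contains, and how far the missing terms could matter.

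**Model content.** Terms named: past-year attempts, study month, CC indicator, Study 2 inclusion, RRT indicator, incarceration offset. Two of these carry information on severity or engagement. The Statistical power paragraph puts six-month risk at 0.204 with a past-year attempt and 0.034 without (0.204/0.034 = 6.0). Study 2 inclusion marks recent contact with a participating BH agency. Neither measures diagnosis or the amount of past care. Section 2.B reports 16% serious mental illness (SMI) and 50% substance use disorder (SUD) among jailed subscribers, so there is clinical variation left to account for.

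**Main simulation** (500,000 subjects per scenario; all effect sizes assumed):
- Severity U is standard normal; the intervention T is randomised 1:1.
- Past-year attempt: log-odds = -2.6 + U (prevalence about 10%).
- Visits: overdispersed Poisson, mean 3 without the intervention, multiplied by 1.5 under T and by exp(a) per SD of U.
- Attempt: log-odds = -3.3 - 0.08 per visit + b per SD of U + 1 for a past-year attempt. There is no direct effect of T. Attempt risk came out at 3.2% to 4.5%.
- Mediated log-OR = (T coefficient without visits) - (T coefficient with visits), as the plan defines it.

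| a, b | Adjusting past attempt only | Adding true severity | Share recovered |
|---|---|---|---|
| 0, 0 | -0.108 | -0.108 | 100% |
| 0.2, 0.3 | -0.086 | -0.109 | 79% |
| 0.4, 0.5 | -0.048 | -0.115 | 42% |
| 0.5, 0.8 | -0.012 | -0.137 | 9% |
| 0.7, 1.0 | +0.011 | -0.145 | -8% |

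The share is column two over column three, before rounding: 0.0857/0.1085 = 79%, 0.0483/0.1149 = 42%, 0.0123/0.1373 = 9%, and +0.0114/-0.1454 = -8%. The visit coefficient moves in step: -0.0640 against -0.0805, -0.0338 against -0.0784, -0.0077 against -0.0827, and +0.0064 against -0.0780. The bias therefore enters through the mediator term. With no confounding the models agree.

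Adding log baseline visits to past-year attempt gives -0.086, -0.056, -0.033 and -0.027 in the four confounded scenarios. This helps but is incomplete.

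**Using the plan's diagnosis mix** (1 million subjects; SMI 16%, SUD 50%, risk 5%, past-attempt OR 5 in the model, intervention raising visits 25%). Mediated share with past attempt only, against the share after adding SMI and SUD:
- SMI/SUD multiply visits by 1.5/1.25, attempt ORs 2/1.5: 30% against 37%.
- Visits by 3/2, ORs 3/2: 15% against 37%.
- Visits by 3/2, ORs 4/2, per-visit OR near 0.97: 0% against 32%.
- No diagnosis effect on visits: 41% against 42%.

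**At N = 43,000** (per-visit OR 0.95, visit multipliers 1.5 to 3, attempt ORs 1.5 to 3), two settings gave 71% and 43% of the adjusted value, with the 95% interval excluding zero in all 100 replicates of each. Milder confounding (visits by 1.25, OR 1.5) retained 91%.

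**Opposite direction.** With SMI/SUD multiplying visits by 0.5 to 0.7 and attempt ORs of 2 to 3, the planned estimate was 1.4 to 1.8 times the adjusted value.

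**Limits.** These simulations adjust for past-year attempts but do not include the Study 2 inclusion term, and CMS calls were not simulated. The 16% and 50% describe all jailed subscribers; the documents do not give the mix among the Study 2 subset.

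**The case against.** A reader might infer that Aim 2 makes no adjustment for illness severity, or that past-year attempts are its only patient-level baseline covariate. The documents do not support either. Past-year attempts are covaried and are a strong risk marker by the plan's own figures, and Study 2 inclusion is a patient-level marker of recent BH care. The planned model may therefore leave less confounding than the simulations, which omit that second term.

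A reader might also infer that the analysis will hide or reverse true mediation. That presumes sicker subscribers use more care after release. No section reports post-release use by diagnosis, and parts of the documents lean the other way: Section 2.A describes arrest as often happening when care has lapsed, and Section 2.B says only about a third of community-linked people with SMI take up expected treatment after jail. If sicker subscribers disengage, mediation is exaggerated. Even in the masking direction, several settings attenuate the effect without hiding it, and at the trial's size the interval still excluded zero in the two settings tested. A sign change appeared only under the strongest confounding tried.

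These objections limit what can be said about direction and size. They do not supply the missing covariates. Past-year attempts alone left a gap in every scenario in which severity affected both visits and attempts.

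**Conclusion.** The concern holds in a limited form. As written, Aim 2 leaves the path from visits and calls to attempts open to residual confounding by severity and care engagement, and the change-in-coefficient estimate can be biased either way. If sicker subscribers use more care, the simulated mediated effect ranges from mildly attenuated to near zero. If they disengage, it is inflated.

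The structural gap rests on the documents. The magnitudes rest on assumed confounding strengths and are illustrative only; nothing in the documents fixes the direction. The change is one that should be made, since Aim 2 carries the mechanism claim. A reader should not extend the problem to the Aim 1 intervention effects, whose estimates do not depend on the mediator.

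**What to change.** In Section 2.C4, prespecify for Aim 2 a common set of baseline covariates from the 12-month historical extract, entered in both the with- and without-mediator models and fitted on the same sample:
- past-year outpatient BH visits and, where available, past-year CMS calls;
- SMI and SUD diagnoses, or a comorbidity measure;
- past-year ED and hospital use;
- past-year arrests;
- demographics.

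Using the same covariates and sample in both models means the change in coefficient reflects the mediator alone. Baseline visits should not be the only addition, since they removed only part of the simulated bias. Report the indirect effect with a sensitivity analysis for unmeasured mediator-outcome confounding, and state that residual confounding remains and that its direction is not known in advance.

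The cost is revised wording and a little more analysis work. Section 2.C4 already lists diagnoses, service use, arrests and demographics in the extract; availability of past-year call counts should be confirmed. The Aim 1 model and its estimates stay as planned.

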This proposal involves two studies of evidence-based suicide prevention practices triggered by CareSource justice notifications, in a 2x2 factorial design. The **first study** will randomize CareSource's ~43,000 Ohio subscribers who pass through jails over 12 months to receive monthly Caring Contact letters sent by CareSource over a 6-month period or to Care as Usual. The **second study** (running simultaneously) will involve a subset of ~6,000 of the 43,000 subscribers passing through jail who were seen in one of 12 large BH agencies in the 6 months prior to jail detention. Using a stepped wedge design, the 12 agencies will be brought online over time, receiving (a) notifications of jail detentions/releases with instructions for re-engaging clients in services; and (b) training in the Safety Planning Intervention plus notification to use it when a subscriber with past *medically treated* suicide attempts (identified by CareSource through claims data) is released from jail.

Specifically, we plan to examine the following:

Aim 1: Evaluate the effectiveness of the implemented study interventions.

Hypothesis 1a: CareSource subscribers who receive CC letters during the 6-month period will have fewer claims related to suicide attempts than subscribers who did not receive CC letters.

Hypothesis 1b: Provider involvement in the reports, re-engagement, and training (RRT) intervention will be associated with a reduction in subscriber claims related to suicide attempts. Further, the addition of flags and recommendations to provide SPI for individuals with past 12 months claims data identified suicide attempts will further reduce suicide attempts.

Aim 2. Examine the number of outpatient behavioral health claims in the 6 months following the index jail release and number of calls to CMS line as mediators of the intervention/s effects on suicide attempts. Mediation will be revealed by the extent to which the intervention effect parameter estimates change with the addition of the putative mediator. We will use bootstrap methods to estimate 95% uncertainty intervals around the mediated effect.

Aim 3. Examine intervention cost-effectiveness and return on investment. We will examine costs (and savings) in future years for both the Caring Contacts and Reports, Re-engagement, and Training (RRT) components of the proposed study.

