Using the IHI Framework for Going to Full Scale,⁶⁶⁻⁶⁷ this project will focus on sustainability and scalability. We will assess, maximize, and optimize intervention: (1) scalability (per the Intervention Scalability Assessment Tool⁶⁸); (2) sustainability (per the Program Sustainability Assessment Tool⁶⁹⁻⁷⁰) (3) feasibility, acceptability, and appropriateness to providers and systems (per the Acceptability of Intervention Measure,⁷¹ Intervention Appropriateness Measure,⁷¹ and Feasibility of Intervention Measure⁷¹); and (4) actual and recommended implementation strategies (via process mapping and implementation process/case notes).

Statistical power. Assumptions. We conducted a simulation study, allowing for variability in release dates, numbers eligible, and introducing a small intra-cluster correlation (ICC = .01). We assumed 43,000 eligible subscribers for Study 1, with 50% randomly assigned to CC. Based on last year's data, we assumed 6,000 eligible subscribers for Study 2. We expect that ~10% of the 6,000 ($n \sim 600$) will have past suicide attempt identifiable through CareSource claims data. We assumed a six-month risk of suicide attempt 0.05, but past 12-month claims data-identified suicide attempt increases this risk (i.e., .034 in absence of past-year suicide attempt, 0.204 with a past-year suicide attempt, odd ratio (OR) = 5), similar to SPIRIT. **Results.** We ran the simulation model 2001 times. Significance was assessed using a two-tailed type-I error level of 5%. Caring Contacts. We will have 85.6% power to detect an effect equivalent to an OR of 0.89. CC has been found to have much stronger effects than this in previous studies²² suggesting that we are adequately powered for CC. RRT. If we assume an intervention effect for Study 2 of 0.87 OR, we will have 88.3% power to detect this effect. For subscribers with a past year suicide attempt within Study 2 (who will be flagged to receive SPI), we will have 96.4% power to detect an OR of 0.63 (the OR detected for SPI in our previous trial, SPIRIT).⁴⁶ Having superadequate power for this test offsets concerns about providers potentially not providing SPI as instructed in this large, real-world study.

D. Material Inducements

Study 1

Provider focus groups: No material inducements will be provided for BH providers who engage in the focus groups. Providers will complete study-related procedures during work time and are typically not able to accept material inducements.

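### Aim 2 measures mediation by the change in a logistic coefficient, which is not zero without mediation: the shift is away from the null, usually small, and understates a mediated benefit

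*Combined protocol and SAP*

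**What the plan says.** Section 2.C4 (Data Analysis, Aim 1) sets the outcome model for medically treated attempts: "The main analysis framework will be logistic regression with the cumulative risk of a claims-data-identified suicide attempts" is the main framework. A count model is secondary: "We will secondarily use a negative binomial model and a count outcome for the number of MT suicide attempts".

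The Aim 2 paragraph of the same section takes outpatient behavioural health claims and "number of calls to the CMS line as mediators of the intervention/s effects on suicide attempts by adding this variable to our effectiveness model". The criterion is: "Mediation is revealed by the extent to which the intervention effect parameter estimates change with the addition of the putative mediator". Section 2.A (Aim 2) repeats it: "Mediation will be revealed by the extent to which the intervention effect parameter estimates change with the addition of the putative mediator". The interval is described as follows: "We will use bootstrap methods to estimate 95% uncertainty intervals around the mediated effect".

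The text does not move the effect to a risk scale or say which direction of change counts as mediation. It also does not make an effect of the intervention on the mediator part of the criterion. Visits and calls are analysed as outcomes elsewhere in 2.C4, but Aim 2 is not tied to those results.

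**The concern.** The null of interest is that nothing is mediated: either the intervention does not move visits or calls, or these do not move attempts. The planned statistic is the intervention coefficient without the mediator minus the coefficient with it. Odds ratios are non-collapsible, so this difference mixes mediation with a purely arithmetical shift. The shift appears whenever the intervention has an effect and the mediator predicts attempts.

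Two consequences follow. An interval may exclude zero and suggest that visits or calls offset the letters' benefit when the letters did not change them. And a real mediated benefit is understated, because the shift has the opposite sign. Section 2.C4 expects a modest intervention effect, and letters may move visits only slightly, so even a shift of a few percent of the coefficient could matter next to the mediated effect being sought.

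**Working it through.** **Plan's own figure.** The documents give no figure for the mediation analysis. The nearest is 85.6% power for Caring Contacts (CC) at OR 0.89. With 21,500 per arm, control risk 0.05 and CC risk 0.0447, the difference is 0.00525 and its standard error is √[(0.05×0.95 + 0.0447×0.9553)/21,500] = 0.00205. Then z = 2.56, and power is Φ(2.56 − 1.96) ≈ 73% two-sided. This does not reproduce 85.6%. The plan's simulation is not described in enough detail to explain the gap, and nothing below depends on it.

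**Inputs from the Statistical power paragraph.** 43,000 subscribers randomised 1:1; CC OR 0.89; RRT OR 0.87 in 6,000; flagged subgroup OR 0.63 in about 600 at risk 0.204. For the overall risk: "We assumed a six-month risk of suicide attempt 0.05". Past attempt is given OR 5, the plan's stated value, and 10% prevalence; the plan states that prevalence for Study 2 only, and it is carried over here to Study 1.

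**Assumptions not in the documents.** The mediator is a skewed count (negative binomial, mean 4, dispersion 0.5, cut at 40; also mean 6, SD 12). Its OR for attempts per SD is varied. It is independent of assignment and unconfounded, and there is no clustering.

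**Formula.** With mediator: logit P(Y) = α + β_c·T + γ·X + δ·M. Without: logit P(Y) = α* + β_r·T + γ*·X. The planned statistic is D = β_r − β_c. There is no mediation by construction, so D should be 0.

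**Population values at CC OR 0.89** (β_c = ln 0.89 = −0.1165; mean-4 mediator):

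| Mediator OR per SD | β_r | D as % of β_c |
|---|---|---|
| 0.5 | −0.1152 | 1.1% |
| 0.667 | −0.1159 | 0.5% |
| 1.25 | −0.1160 | 0.5% |
| 1.5 | −0.1140 | 2.2% |
| 2 | −0.1059 | 9.1% |

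For OR 2: (−0.1059 + 0.1165)/0.1165 = 0.0106/0.1165 = 9.1%. With the mean-6, SD-12 mediator, expressed as a share of β_r, the shift is 3.5% at OR 1.5 and 14% at OR 2. If the intervention has no effect, D is exactly 0.

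**Share of 95% percentile-bootstrap intervals excluding zero** (1,500 trials, 200 resamples each, mean-4 mediator). Away means the coefficient moves away from the null when the mediator is added; toward is the direction of a mediated benefit. With no intervention effect the two columns are simply the two tails. The last column is the natural indirect effect on the risk-difference scale, same data and bootstrap.

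| N | Intervention OR | Mediator OR per SD | Away | Toward | Total | Risk scale |
|---|---|---|---|---|---|---|
| 43,000 | 1.00 | 2 | 2.8% | 3.0% | 5.8% | 5.6% |
| 43,000 | 0.89 | 0.5 | 5.3% | 1.9% | 7.3% | 5.6% |
| 43,000 | 0.89 | 0.667 | 4.3% | 1.7% | 5.9% | 5.5% |
| 43,000 | 0.89 | 1.5 | 6.3% | 1.1% | 7.3% | 6.7% |
| 43,000 | 0.89 | 2 | 11.8% | 0.3% | 12.1% | 5.3% |
| 43,000 | 0.63 | 1.5 | 27.9% | 0.2% | 28.1% | 6.0% |
| 6,000 | 0.87 | 2 | 5.5% | 1.3% | 6.8% | 5.3% |
| 600 (risk 0.204) | 0.63 | 2 | 11.5% | 0.3% | 11.9% | 6.5% |

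Monte Carlo error near 5% is √(0.05×0.95/1,500) ≈ 0.6 points. With the mean-6, SD-12 mediator the totals at CC OR 0.89 are 7% (mediator OR 1.5) and 16% (mediator OR 2), and 36% at CC OR 0.80 with mediator OR 2.

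**Understatement when mediation is real.** In a further calculation of the same kind, CC raises visits by 2% and visits are protective (OR 0.5–0.67 per SD). The planned statistic then understates the mediated log-odds change by about 17–24%. With 5% more visits it understates it by 7–10%.

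**The case against.** A reader might infer that the trial is likely to announce mediation that does not exist. The documents do not support that. A mediated benefit shrinks the coefficient toward zero, and the artefact does the opposite: false exclusions in the mediation direction fall below the nominal 2.5% whenever the intervention has an effect. The hypotheses in Section 2.A are directional, so a careful analyst would see apparent suppression.

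The artefact is also small at the planned effect unless the mediator strongly raises risk, and the trial's rationale is that re-engagement lowers it. The larger rates rest on mediator strengths and CC effects that the documents do not give. The power paragraph does say that "CC has been found to have much stronger effects than this in previous studies", but attaches no figure. If visits predict attempts because sicker people use more care, that is confounding, which would affect a risk-scale analysis too.

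Finally, the trial will estimate directly whether CC changed visits and calls. The secondary count model, with the usual log link (not stated), is free of this artefact. The plan also sets no significance rule for mediation.

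Most of this stands and limits the size of the point. It does not remove it. The outcome analyses and the secondary model do not correct the Aim 2 statistic, the criterion is worded without a sign, and the understatement of a true mediated benefit remains even for a protective mediator.

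**Conclusion.** The point holds in a limited form. The planned statistic does not equal zero under no mediation whenever the intervention has an effect and the mediator predicts attempts. The error appears as suppression and as understated mediation of a benefit. It turns into declared mediation only if the size of the change is read without its sign, which the current wording allows.

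At CC OR 0.89 it is negligible for a weak or protective mediator, minor at a mediator OR of 1.5 per SD, and material only for a strong risk-increasing mediator. A stronger CC effect raises the false exclusion rates. For RRT in 6,000 subscribers it is slight even with a strong mediator. All sizes depend on the assumed mediator distribution and its association with attempts, and on simulations without clustering or confounding.

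A change is worth making because Aim 2 is a named aim and the better method is cheap.

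**What to change.** In Section 2.A (Aim 2) and the Aim 2 paragraph of 2.C4, define the mediated effect as the natural indirect effect on the risk-difference scale. Fit a model for the mediator and keep the existing logistic outcome model with its covariates and offset. Hold assignment fixed, and average the predicted risks over the mediator distribution under intervention and then under control. The difference is the mediated effect, and it is zero when the two mediator distributions agree. Bootstrap that quantity.

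State that a negative value (lower risk through the mediator) is mediation of a benefit, and report the intervention's effect on visits and calls beside it. Keep logistic regression for the Aim 1 tests. Standardisation is preferable to refitting a linear risk model, because the days-incarcerated offset does not carry over directly to the linear scale.

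The cost is a few sentences, one extra mediator model and some code, with the same data. Mediated effects will be reported as risk differences rather than odds ratios. The change does not deal with confounding of the mediator by severity, or with the mediator being counted over the same six months as the attempts.
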